6.2.2.3.3 Visit 4 (day 22)

Visit 4 (day 22) is the last visit in the repeated treatment cycle. This visit may coincide with day 1 of the following treatment cycle. Examinations which are due at both the present visit and the day of volasertib administration need only to be documented once:

- Physical examination
- ECOG performance score
- Body weight
- Vital signs
- Occurrence of AEs since last visit
- Changes in concomitant therapy
- Safety lab parameters (without urinalysis)
- Coagulation parameters
- Tumour assessment at the end of each cycle
- Review of patient eligibility for repeated treatment cycles
- pregnancy test after every other cycle for women of childbearing potential - women of childbearing potential (premenopausal female patient) is defined as the female patient who is not surgically sterilised by hysterectomy or bilateral tubal ligation, or post-menopausal for at least 12 months.

6.2.3 End of trial and follow-up period

6.2.3.1 Visit at the end of treatment

The end of treatment (EOT) information should be obtained when the patient concludes active treatment in the trial, along with the information obtained at the visit scheduled for that time point. If the patient concludes the trial mid-way through a treatment cycle and not at the end of a treatment cycle, the required end of cycle information should also be collected at this time.

The following will be obtained and / or performed:

Proprietary confidential information.

© 2017 Boehringer Ingelheim International GmbH or one or more of its affiliated companies. All rights reserved.
This document may not - in full or in part - be passed on, reproduced, published or otherwise used without prior written permission.

- Termination of patient's active treatment (including reason for termination or if applicable premature discontinuation of trial, date of last administration of the trial drug)
- Patient status: in case the patient had PD the date of first diagnosis of PD has to be recorded
- Physical examination, ECOG score, body weight, and vital signs
- ECG
- Safety laboratory, including coagulation parameters and urinalysis
- Occurrence of AEs since last visit
- Changes in concomitant therapy
- Clinical tumour assessment

6.2.3.2 Follow-up visit

Follow-up visits will be performed after the EOT visit for patients who are not eligible for further treatment cycles until progression of disease, death, treatment with any other anti-tumour therapy, patient is lost to follow-up, or agreement between sponsor and principal investigator not to pursue further follow up visits.

Follow-up visits should be performed at 3 months intervals or earlier if appropriate. Follow-up visits may also be performed by telephone interview in case the patient is unable to visit the investigator.

The following will be obtained and / or performed.

- Occurrence of AEs since last visit in case they are considered drug-related
- Follow-up of AEs in case they were not yet recovered at EOT
- ECOG performance score
- Treatment with any other anti-tumour drug
- Patient status: date of and reason for death (if applicable), date of progression (in case, the patient experienced PD)

If visit is performed by telephone interview at least information on progression, date of progression and date of death should be obtained.

After approval of Protocol Revision 3, Follow-up is completed 21 days after discontinuation of study drug.

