Proprietary confidential information.

© 2017 Boehringer Ingelheim International GmbH or one or more of its affiliated companies. All rights reserved.
This document may not - in full or in part - be passed on, reproduced, published or otherwise used without prior written permission.

SUBSEQUENT TREATMENT CYCLES (for patients with clinical benefit)

Study period	Treatment				EOT ¹	FU ²
Visit	V1	V2 ⁶	V3 ⁶	V4 ⁷		
Day	1	8	15	22		
(day range)		(±1)	(±1)	(±2)		
Physical examination ¹⁰	X			X	X	
ECOG performance score ¹⁰	X			X	X	X
Body weight ¹⁰	X			X	X	
Vital signs ¹⁰	X	X	X	X	X	X
ECG	X ³				X	
Tumour assessment ⁸	X			X	X	
Infusion of volasertib	X					
Safety lab parameters ⁴	X	X	X	X	X	
Coagulation parameters ⁴	X			X	X	
Pregnancy test ⁹				X		
Adverse events	X	X	X	X	X	X ²
Concomitant therapy	X	X	X	X	X	
Termination of trial medication					X	
Treatment with any other anti-tumour drug						X
Patient status					X	X
Eligibility for further treatment cycle	X			X		

1. EOT, end of treatment. Assessments which are to be performed at the last visit (when a patient discontinues the study treatment)
2. FU, follow-up. Follow-up visit should be performed 21 days after discontinuation of study drug
3. ECG on visit V1 should be performed according to [5.2.4](#). After approval of the Protocol revision 3, ECG should be performed prior to and at the end of volasertib infusions as single reads using a local ECG machine. No central analysis of ECGs will be performed.
4. Safety lab includes haematology and serum biochemistry. For detail see [5.2.3](#). Urinalysis (dipstick) is only performed at EOT. After approval of the Protocol revision 3, safety laboratory including coagulation parameters should be done only as medically indicated at discretion of the investigator. The results should be recorded in the source data only; documentation in the eCRF is not required.
5. In case adverse events were not yet recovered at the EOT visit or if new AEs occur that are considered drug related
6. Optional visits at the investigators discretion, can be performed by phone as well
7. Visit V4 may coincide with V1 of the following cycle in case the patient continues the study treatment
8. Clinical response assessment after every cycle, radiological assessment at the investigator's discretion. After implementation of the Protocol revision 3, this efficacy data will be recorded in the source data only; documentation in the eCRF is not required.

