5.2.2.2 Adverse event and serious adverse event reporting

All adverse events, serious and non-serious, occurring during the course of the clinical trial (i.e., from signing the informed consent onwards through the observational phase (=21 days after last drug administration)) will be collected, documented and reported to the sponsor by

Proprietary confidential information.

© 2017 Boehringer Ingelheim International GmbH or one or more of its affiliated companies. All rights reserved.
This document may not - in full or in part - be passed on, reproduced, published or otherwise used without prior written permission.

the investigator on the appropriate eCRFs / SAE reporting forms. After this defined observational period only AEs and SAEs related to the study drug and/or study design have to be reported by the investigator. Reporting will be done according to the specific definitions and instructions detailed in the ‘Adverse Event Reporting’ section of the Investigator Site File.

For each adverse event, the investigator will provide the onset date, end date, intensity, treatment required, outcome, seriousness, and action taken with the investigational drug. The investigator will determine the relationship of the investigational drug to all AEs as defined in [section 5.2.2.1](#).

The investigator also has the responsibility to report any AEs occurring once informed consent has been signed and through 21 days after last dose of study administration. Any AEs reported to the sponsor during this phase must be documented in the safety database. AEs that are not yet recovered at the End of Treatment (EOT) visit will be followed until recovery or, in case of persistence, sufficient characterization of the toxic effects has been achieved and the investigator and the BI Clinical Monitor agree not to pursue them further.

Table 5.2.2.2:1 AE/SAE reporting requirements

Time period	Reporting requirements
Screening until 21 days after last drug intake	Report all AEs, SAEs regardless of relatedness. This includes all deaths.
Post-treatment (>21 days after last drug intake)	Report AEs and SAEs which are considered related to study drug or study design/ procedures. Please note: Acc. to this rule also Death will only be reported as SAE if considered study drug or study design/procedure related.

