7.8.1 Adverse Events

The analysis of adverse events will focus on events that occurred during the on-treatment period, defined from the first treatment administration until 21 days after the last administration for all patients who receive at least one administration of the study treatment regimen. Tables will display the results within each cohort defined by the starting dosage of volasertib.

The analysis of adverse events will be performed within each of the following three time periods separately ([Section 6.1](#)):

- First cycle volasertib+ itraconazole combo-therapy period
- Second cycle volasertib mono-therapy period
- Continued volasertib mono-therapy period.

The AEs occurred during screening period, itraconazole induction period, and post-study period ([Section 6.1](#)) will be listed.

Standard tabulations arranged by MedDRA SOC and preferred term (PT) will include:

- the overall incidence of adverse events (AE)
- AE intensity graded according to the common terminology criteria for adverse events (CTCAE) version 3

- AE judged to have been related to trial medication
- AE leading to dosage reduction
- AE leading to permanent treatment discontinuation
- AE identified associated with the protocol-specified significant event
- Serious AE

Listings will be produced for the following AEs

- Infections

Listings will be prepared of patients who are identified as having experienced any of the following AEs. Identification will be based upon modified MedDRA SMQ and HLT groupings.

- Mucositis
- QT prolongation
- Cardiac, combining the following SMQ
 - Cardiac failure
 - Ischaemic heart disease
 - Cardiac arrhythmia terms
- Hemorrhages SMQ
- Hepatic
 - AE identified by the SMQ
 - Listing of all ALT, AST, Tbili, and ALK over time, for patients with
 - 1) any ALT or AST ≥ 3 x ULN combined with elevation of total bilirubin ≥ 2 x ULN at the same time or
 - 2) an isolated elevation of AST and/or ALT ≥ 5 x ULN (without an elevation of bilirubin)

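### The follow-up visit asks only for drug-related new AEs and unresolved old ones, which contradicts the rule to collect all AEs to 21 days after the last dose when EOT falls before day 22

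*Protocol*

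**What the plan says.** **Reporting duty.** Protocol 5.2.2.2 makes the investigator responsible to "report any AEs occurring once informed consent has been signed and through 21 days after last dose of study administration". For the period from screening to 21 days after the last drug intake, Table 5.2.2.2:1 states: "Report all AEs, SAEs regardless of relatedness. This includes all deaths". Only after that does relatedness to study drug or study design/procedures decide what is reported.

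**Analysis window.** Protocol 7.3.3 counts an AE within 21 days of the most recent volasertib infusion as on treatment. SAP 7.8.1 uses an on-treatment period "defined from the first treatment administration until 21 days after the last administration". For a patient who stops after cycle 1 or cycle 2, SAP 6.1 closes that cycle's period 21 days after the infusion.

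**Visit lists.** EOT takes place when active treatment ends. Protocol 6.2.3.1 foresees an early one ("If the patient concludes the trial mid-way through a treatment cycle and not at the end of a treatment cycle") and then brings the end-of-cycle data forward to it. The AE question at EOT has no relatedness filter. The follow-up visit in 6.2.3.2 does have one: "Occurrence of AEs since last visit in case they are considered drug-related", together with "Follow-up of AEs in case they were not yet recovered at EOT". Footnote 5 to the flow chart for subsequent cycles says the same: "In case adverse events were not yet recovered at the EOT visit or if new AEs occur that are considered drug related".

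**Follow-up timing.** Section 6.2.3.2 keeps three-monthly follow-up in its general text and adds that, after Revision 3, follow-up is complete 21 days after study drug is discontinued. A telephone follow-up needs to cover only progression and death as a minimum.

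**The concern.** A relatedness filter at follow-up makes sense once the 21-day window has closed, because Table 5.2.2.2:1 applies a similar filter from then on. But the follow-up question looks back to the last visit, which for an early stopper is EOT. If EOT comes before day 22, the question reaches into days on which all AEs are due and which the SAP analyses as on treatment.

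A patient who completes a cycle does not have this problem. In subsequent cycles, the day 22 list (6.2.2.3.3) and the next infusion visit (6.2.2.3.1) both ask about AEs without a filter. The gap therefore falls on those who stop mid-cycle.

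Safety and tolerability are secondary objectives (Protocol 2.2). SAP 7.8.1 tabulates overall AE incidence and CTCAE intensity by treatment period and by starting-dose cohort. With 24 patients planned, a few unrecorded events can change a row. Whether they are recorded could depend on when the patient stopped and on the investigator's view of causality, although both documents intend to report all AEs.

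**Working it through.** The plan gives no figure to reproduce. The check compares the passages and then counts days.

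**1. Which rule applies after EOT?** Section 3.3.4.1 sends patients who end active treatment, but stay in the trial, to section 6.2.3. After EOT, the contact listed there is the follow-up visit.

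| Time after the last infusion | 5.2.2.2 and Table 5.2.2.2:1 | Visit list | Agree? |
|---|---|---|---|
| Up to EOT | all AEs | all AEs | yes |
| EOT to 21 days | all AEs | new AEs only if drug-related; AEs unresolved at EOT | no |
| After 21 days | related to drug or to design/procedures | new AEs only if drug-related; AEs unresolved at EOT | broadly |

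**2. How many days are in conflict?** Take the infusion as day 1, so that the window closes on day 22. With EOT on cycle day d (d ≤ 22):

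uncovered days = 21 − (d − 1) = 22 − d

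- d = 8: 22 − 8 = 14 of 21 days (67%)
- d = 15: 22 − 15 = 7 of 21 days (33%)
- d = 22: 22 − 22 = 0

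The values of d are illustrative. Days 8 and 15 are scheduled visit days. In cycle 1 the flow chart places the review of eligibility for a further cycle on day 15, so EOT around then is plausible.

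**3. Did Revision 3 close the gap?** It moved the end of follow-up to 21 days after discontinuation and left the AE item unchanged. If discontinuation means the last dose, all of follow-up now lies inside the all-AE window, and the related-only question has no period in which it agrees with 5.2.2.2.

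**4. Does the meaning of the last drug matter?** Table 5.2.2.2:1 refers to drug intake without naming the drug. Protocol 7.3.3 and SAP 6.1 refer to volasertib. Itraconazole is planned to day 15 of cycle 1. If it counts, the reporting window after a full course ends on day 15 + 21 = day 36, and even an EOT on day 22 leaves 36 − 22 = 14 reporting days under the narrower question. The volasertib-based analysis window would still close on day 22.

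**5. Which events are exposed?** Remove everything collected by another route:

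- SAEs go to the sponsor immediately, whatever the causality (5.2.2.2).
- Protocol-specified hepatic events are expedited in the same way (5.2.2.1).
- Drug-related new AEs and AEs unresolved at EOT are on the follow-up list itself.
- DRTs are drug-related by definition, and the MTD is defined from DRTs (5.2.6).
- The PK endpoints do not use AE data.

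This leaves new, non-serious AEs judged unrelated, with onset between EOT and 21 days after the last dose.

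**6. After the fix.** If follow-up asks for all AEs to 21 days after the last dose, the uncovered days are 0 for every d.

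**The case against.** The strongest reply is that 5.2.2.2 already settles the matter. It states the 21-day duty more than once, and a list of visit procedures does not waive it. This stands in large part: a site that follows 5.2.2.2 loses nothing. A reader might infer from the visit list that on-treatment AEs are in fact under-recorded in early stoppers. The documents do not support that. They show two inconsistent instructions and hence a risk that depends on which one a site works from.

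Second, 3.3.6 asks for the next scheduled visit as well as EOT when a patient is withdrawn from the trial. This also stands in part. The visit lists for subsequent cycles ask about AEs without a filter. But 3.3.6 is qualified by feasibility, it is worded for withdrawal from the trial rather than from active treatment, and the next scheduled visit may itself fall before day 22.

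Third, the percentages measure calendar days, not lost events. This is correct. The documents give no AE rate, no split by causality and no frequency of mid-cycle stops, so no count of missing events can be derived.

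Fourth, footnote 5 belongs to the chart for subsequent cycles and adds little for cycles 1 and 2. That is fair, but 6.2.3.2 is not limited to later cycles and carries the point alone.

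A reader might also connect the gap with the statement in SAP 7.4 that two of the first three patients treated at 300 mg discontinued. The SAP says they did so after cycle 1 and gives no EOT dates. It does not show that either stopped mid-cycle, so it is not evidence that the 300 mg tables are incomplete.

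**Conclusion.** The contradiction is real but small. Whenever EOT falls before day 22, Protocol 6.2.3.2 and footnote 5 ask for less than 5.2.2.2, Table 5.2.2.2:1 and the 21-day on-treatment window in Protocol 7.3.3 and SAP 6.1/7.8.1 require. The exposed period is 22 − d days: 14 for EOT on day 8, 7 for day 15, none for day 22. This assumes that the last dose is the volasertib infusion, that no further scheduled visit takes place after EOT, and that the site works from the visit list.

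Only new, non-serious AEs judged unrelated are at risk. The outputs concerned are the overall AE incidence and intensity tables, which may be less complete for patients who stop early than for those who continue. The conclusions on dose, the related-AE and serious-AE tables and the PK comparison do not depend on this wording. It is still worth correcting, because the written rule makes completeness depend on who stops and the correction costs almost nothing.

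**What to change.** 1. Reword the AE item in Protocol 6.2.3.2, for example: *All AEs since EOT with onset up to 21 days after the last drug administration, whether or not considered related; after that, only AEs considered related to study drug or to study design/procedures.* Keep the item on AEs unresolved at EOT.
2. Make flow chart footnote 5 say the same.
3. State in 5.2.2.2 and 6.2.3.2 whether the last drug means volasertib only or also itraconazole, so that the reporting window and the analysis window can be compared.
4. Add AEs to the minimum content of a telephone follow-up. If the follow-up visit falls before the window closes, obtain the remainder by telephone. Section 6.2.3.2 now allows telephone follow-up only for patients who cannot attend, so that condition needs a short extension.

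The cost is a few sentences in the protocol, a few more AE entries for patients who stop mid-cycle, and possibly one telephone contact for each of them. No SAP change is needed, since its on-treatment window already matches 5.2.2.2 if the last drug is volasertib.

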6.2.3.3 End of trial

The clinical trial will be considered completed as soon as the last patient has died or was lost to follow-up. If patients are still on treatment at the time the trial report is written, these patients will either be included in a follow-up trial or alternatively kept on treatment in this trial. If patients are kept on treatment in this trial then additional data will be reported in an adequate format in appropriate reporting timelines after all of these patients will have completed follow-up.

Proprietary confidential information.

© 2017 Boehringer Ingelheim International GmbH or one or more of its affiliated companies. All rights reserved.
This document may not - in full or in part - be passed on, reproduced, published or otherwise used without prior written permission.

7. STATISTICAL METHODS AND DETERMINATION OF SAMPLE SIZE

7.1 STATISTICAL DESIGN - MODEL

Objectives

The primary objective of the present study is to investigate the influence of co-administration of itraconazole, a potent dual inhibitor of cytochrome P450 3A4 and P-gp, and volasertib (Test, T) on the pharmacokinetic profile of volasertib without co-administration of itraconazole (Reference, R). Therefore the relative bioavailability of volasertib will be assessed.

Design

The study will be conducted according to an open-label, randomised, fixed sequence design. The comparisons will be intra-individual (each subject serves as his own control) and the precision is therefore expected to be higher than with a between-subject comparison [[R94-1529](#)]. The uncontrolled design with respect to potential time effects is unavoidable but still expected to deliver valid results on the volasertib PK.

Primary endpoints

Relative bioavailability of volasertib and its main metabolite CD 10899 is primarily to be determined on the basis of the parameters AUC_{0-tz} , and C_{max} (see [Section 5.5.1](#)). The derivation of these primary parameters is given in the internal SOP 029-DCP-102.

Secondary endpoints

The $AUC_{0-\infty}$ of volasertib and its main metabolite CD 10899 will be statistically assessed using the same methods as described for the primary endpoints.

The derivation of these PK parameters is presented in the internal SOP 029-DCP-102.

Safety and tolerability will be determined on the basis of the following parameters: adverse events, ECG, and clinical lab tests.

Proprietary confidential information.

© 2017 Boehringer Ingelheim International GmbH or one or more of its affiliated companies. All rights reserved.
This document may not - in full or in part - be passed on, reproduced, published or otherwise used without prior written permission.

The derivation of these PK parameters is presented in the internal SOP 001-MCS-36-472_RD-01.

If deemed necessary, statistical assessments will be conducted.

Model

The statistical model used for the analysis of the primary and secondary PK endpoints will be an ANOVA (analysis of variance) model on the logarithmic scale. This model will include effects accounting for the following sources of variation: 'subject' and 'treatment'. The effect 'subject' will be considered as random, whereas the 'treatment' effect will be considered as fixed. For tests on treatment effects, the denominator sum of squares will be the sum of squares for error in the comparison R – T. The model is described by the following equation

$y_{km} = \mu + s_m + \tau_k + e_{km}$, where

y_{km} = logarithm of response measured on subject m receiving treatment k,

μ = the overall mean,

s_m = the effect associated with the mth subject, $m = 1, 2, \dots, n$,

τ_k = the kth treatment effect, $k = 1, 2, \dots$,

e_{km} = the random error associated with the mth subject who received treatment k.

The subdivision into male / female subjects is not expected to have influence on the intra-individual treatment comparisons and therefore 'sex' is not a model term.

In case the MTD of co-administration of itraconazole and volasertib is less than 300mg, dose will be considered in the ANOVA model to correct for the different starting doses of the patients. The model will take into account the dose proportionality established for volasertib.

7.2 NULL AND ALTERNATIVE HYPOTHESES

The relative bioavailability of volasertib in combination with itraconazole compared volasertib alone will be investigated descriptively by applying the average bioequivalence method to the ratio between PK parameters (AUC_{0-tz} and C_{max}). No confirmatory hypothesis will be tested.

Proprietary confidential information.

© 2017 Boehringer Ingelheim International GmbH or one or more of its affiliated companies. All rights reserved.
This document may not - in full or in part - be passed on, reproduced, published or otherwise used without prior written permission.

